5. ANALYSIS POPULATIONS

As Treated (i.e. Safety [SAF]) Population

The as-treated population will comprise all randomized participants and their infants who received any study treatment grouped by actual treatment received, irrespective of amount or duration of treatment received. Unless specified otherwise, data for this population will be analyzed as available (i.e. irrespective of protocol deviation occurrence, subsequent study participation termination, or study drug withdrawal).

Intention to Treat (ITT) Population

The primary analysis population will be the ITT population, which will include all randomized participants and their infants. All participants will be assigned to the arm to which they were randomized irrespective of treatment received. Unless specified otherwise, all participants will be included in analyses using this population (with data as available or imputed when specified per

section 7.3 and irrespective of protocol deviation occurrence, subsequent study participation termination, or study drug withdrawal).

High Risk for Infection (HR) Population

The HR sub-group will include all women in the ITT and their infants meeting criteria for being high risk (i.e., prolonged labor [≥ 18 hours] and/or rupture of membranes [≥ 8 hours]) at the time of randomization. All participants will be assigned to the arm to which they were randomized irrespective of treatment received. Unless specified otherwise, all participants will be included in analyses using this population (with data as available or imputed when specified per section 7.3 and irrespective of protocol deviation occurrence, subsequent study participation termination, or study drug withdrawal).

Per Protocol (PP) Population

This population will be used to conduct sensitivity analyses for the primary outcome. This population will include randomized participants that received all planned study drug and did not throw up within 15 minutes of taking study drug. Any individuals subsequently identified as ineligible for the study or who were documented as receiving azithromycin during study follow-up excluding study drug will be excluded. Participants will be grouped by actual treatment received. Additional exclusion reasons may be identified after completion of participant enrollment.

The final determination of HR and PP analysis population membership will be via a masked data review prior to final study analyses in order to address any potential anomalous cases that may arise in this large of a study population (e.g. randomization/treatment of a woman who is discharged prior to delivery due to false labor or unresponsiveness to induction). Final decisions with respect to populations used for the interim analyses as well as the final study analyses will be documented in an addendum to this SAP.

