1.6.3 Other Important Considerations

A recurrent concern regarding the potential routine use of azithromycin in a large population is antibiotic resistance. Monitoring for characteristics suggestive of resistant infection will be important to incorporate in the protocol. However, a number of factors mitigate concerns about antibiotic resistance: (a) the design of the trial using a single prophylactic dose (as opposed to recurrent treatment doses) of antibiotic, (b) surveillance of maternal clinical cultures up to 6 weeks in the trial in cesareans in the US revealed that positive wound cultures overall and those positive for resistant organisms were significantly less frequent in the azithromycin group;¹³ (c) if successful, prophylaxis will reduce the risk of infection and actually reduce the overall frequency of use of antibiotics to treat infection (a result in the US trial as stated above). It is estimated that women in the high-risk for infection group as defined will account for about 10-20% of laboring women. In principle, the use of single prophylactic dose (as opposed to multiple) minimizes the likelihood of antimicrobial resistance but samples will be taken to determine antimicrobial resistance.³²

Azithromycin is currently recommended to treat or prevent several infections in pregnancy including gonorrhea (1 g po), chlamydia (1 g po), and *Mycobacterium avium* complex prophylaxis (600 mg twice/week or 1.2 g weekly po). Azithromycin is sometimes used for perioperative prophylaxis in patients at risk for endocarditis (500 mg po). Considering the success with a single dose of 2 g in the Gambian trial, our success with 500 mg IV for cesarean prophylaxis, and the 40% bioavailability of oral azithromycin, we propose to use 2 g po of azithromycin for the proposed intervention. The best approach to this evaluation in order to influence future uptake into clinical practice is an RCT. The primary maternal outcome will be maternal death or sepsis within 42 days after delivery. The primary neonatal outcome will be intrapartum/neonatal death or sepsis within 28 days after birth (defined by WHO criteria).³³

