3. STUDY OBJECTIVES AND OUTCOMES

3.1 Primary Hypothesis and Associated Outcomes

This study had two primary hypotheses, one with a maternal focus and one with a neonatal focus.

1. First, a single, prophylactic intrapartum oral dose of 2 g azithromycin given to women in labor in low and middle-income settings will reduce maternal death or sepsis.
2. Second, a single, prophylactic intrapartum oral dose of 2 g azithromycin given to women in labor in low and middle-income settings will reduce intrapartum/neonatal death or sepsis.

The primary outcomes are:

1. Maternal: Incidence of maternal death or sepsis within 6 weeks (42 days) post-delivery in intervention vs. placebo group.
2. Neonatal: Incidence of intrapartum/neonatal death or sepsis within 4 weeks (28 days) post-delivery in intervention vs. placebo group.

Maternal sepsis is a life-threatening condition defined as organ dysfunction resulting from suspected or confirmed infection that occurs post-randomization during labor or the postpartum period. This WHO definition, endorsed by multiple global health organizations, will be operationalized as suspected or confirmed infection based on the presence of fever ($>100.4^{\circ}\text{ F}/38^{\circ}\text{ C}$) or hypothermia ($<96.8^{\circ}\text{ F}/36^{\circ}\text{ C}$) plus one or more signs of mild to moderate organ dysfunction including tachycardia (≥120 bpm), low BP (systolic <90 mm Hg), tachypnea (>24 breaths/min), altered mental status/confusion, reduced urinary output (<500 cc over 24 hours), jaundice, or renal failure (>1.2 mg/dl). Components of peripartum infection which will be considered in making the diagnosis of suspected or confirmed infection include clinical chorioamnionitis, endometritis, wound infections (perineal or Cesarean), abdominal or pelvic abscess, mastitis/breast abscess or infection, pyelonephritis, pneumonia, and other bacterial infection.

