Neonatal sepsis is defined as a newborn with proven or possible serious bacterial infection (pSBI) or pneumonia, meningitis, urinary tract infection, or omphalitis. Possible serious bacterial infection will be determined using WHO criteria of pSBI defined as severe chest in-drawing, fever (temperature $\geq 100.4^{\circ}\text{ F}/38^{\circ}\text{ C}$), hypothermia (temperature $<95.9^{\circ}\text{ F}/35.5^{\circ}\text{ C}$), no movement at all or movement only on stimulation, feeding poorly or not feeding at all, and/or convulsions. Clinical and laboratory signs of infection will also be considered in making the diagnosis of suspected or confirmed infection.

Only infections that occur post-randomization will count as study outcomes.

Masked adjudication of key infection outcomes will be implemented by the DCC and investigators during the trial to standardize and enhance the reproducibility of trial results. In addition to the above specified criteria, reported antibiotic treatment and culture status will also be considered as part of the adjudication process in making the diagnoses for both maternal and neonatal sepsis. Local site investigators will review and validate the diagnosis for all participants identified to have the primary outcomes applying pre-specified criteria. These reviews will be conducted masked to treatment group. If a case requires additional input and cannot be adjudicated locally, then it will

move to central adjudication where the study PIs will review the participant's information and make a final outcome determination. A random portion of the locally adjudicated cases will be selected for central review to ensure there are no systemic site difference in adjudication. This process will be coordinated by the DCC.

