9.3 Primary Analysis

The primary outcomes of incidence of maternal death or sepsis and incidence of intrapartum/neonatal death or sepsis will be compared between the two treatment arms using generalized linear models. These generalized linear models will be fit with each binary outcome separately as the outcome measure. Estimates of relative risk and associated 95% confidence intervals will be reported. The model will include terms for treatment and site. As randomization occurs at the pregnancy level and approximately 1-2% of pregnancies are anticipated to be multiple gestations, models for neonatal outcomes will account for correlation among multiples assuming an exchangeable covariance structure. If a model for neonatal outcomes has convergence issues, then the generalized linear model will be fit without the adjustment for correlation among multiples. For the two primary outcomes, these analyses will be conducted using the ITT population and the p-values associated with the treatment term will be used to formally test each of the two primary hypotheses at the alpha = 0.05 level.

The primary analyses using the ITT population will use multiple imputation for missing outcomes implemented separately for mothers vs. infants via logistic regression imputation using site and high-risk status prior to randomization as covariates. As sensitivity analyses, the primary outcomes will also be analyzed without imputation for individuals in the ITT population, without imputation for individuals in the per-protocol population; and in the ITT population assuming all missing outcomes are sepsis or death as well as assuming all missing outcomes are not sepsis nor death.

As secondary analyses of the primary outcomes, the models will be run including region (Africa, Latin America, or Asia) and a treatment by region interaction term. If the interaction term has a $p<0.1$, then effect estimates and associated confidence intervals will be reported by region with treatment effect within region for Africa and Asia tested at the 0.025 level.

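### The per-protocol set excludes any non-study azithromycin during follow-up regardless of timing or indication, so it can drop women because they had the primary outcome

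*Combined protocol and SAP*

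**What the plan says.** SAP section 5 builds the per-protocol set from randomized participants who took all planned study drug and did not vomit within 15 minutes. It removes those later found ineligible, and also any individual "documented as receiving azithromycin during study follow-up excluding study drug will be excluded". No timing, indication or order relative to an outcome event is mentioned, and further exclusion reasons may be added after enrollment ends.

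On the role of the set, the same section says: "This population will be used to conduct sensitivity analyses for the primary outcome". The variable table in SAP section 9.2 lists it for both composite outcomes, and SAP section 9.3 includes among its sensitivity analyses one done "without imputation for individuals in the per-protocol population". The formal tests lie elsewhere: "The primary analysis population will be the ITT population".

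The maternal outcome is given in SAP section 3.1 as "Maternal: Incidence of maternal death or sepsis within 6 weeks (42 days) post-delivery", and scheduled follow-up also runs to day 42 (SAP section 4.1). The neonatal outcome closes at day 28. SAP section 5 adds that the "final determination of HR and PP analysis population membership will be via a masked data review", with decisions recorded in a SAP addendum. Section 3 of the protocol lists three populations and no per-protocol set, so it supplies no exception either.

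**The concern.** A per-protocol set should differ from ITT because of adherence and eligibility. Azithromycin after delivery may be contamination, but it may also be a response to suspected infection. In the second case the exclusion lies downstream of the outcome.

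The documents make that link plausible. In sepsis adjudication, "reported antibiotic treatment and culture status will also be considered as part of the adjudication process" (SAP section 3.1). Section 1.6.3 of the protocol says "Azithromycin is currently recommended to treat or prevent several infections in pregnancy", and section 1.5 describes activity against bacteria associated with maternal infection and sepsis. Any maternal antibiotic use to day 42 is itself a secondary outcome that the trial hopes to reduce, and follow-up azithromycin is part of it.

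At stake is the use of one supporting analysis. It could depart from ITT, or agree with it, for reasons unrelated to adherence, and a reader could not tell which.

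**Working it through.** **Inputs from the documents.** Total 34,000, allocated 1:1, so 17,000 per arm; loss to follow-up 2% to 3%; maternal risk 3% on placebo; 20% reduction, so 2.4% on azithromycin and RR 0.80; two-sided alpha 0.05 (SAP sections 4.3, 6.1 and 7.5).

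**Input not in the documents.** The share *f* of outcome cases in each arm that receive non-study azithromycin and are therefore excluded. The values below are assumptions.

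**Step 1: the plan's own figure.** Table 1 gives 15,334 per arm for 3%, a 20% reduction and 90% power. With the pooled-variance formula and mean risk 0.027:

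n = [1.960 × √(2 × 0.027 × 0.973) + 1.282 × √(0.03 × 0.97 + 0.024 × 0.976)]² / 0.006² = 15,334.

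This matches, so the same method is used for power below.

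**Step 2: expected cases with no exclusion.** At 2.5% loss, 17,000 × 0.975 = 16,575 evaluable per arm. Expected cases are 16,575 × 0.03 ≈ 497 on placebo and 16,575 × 0.024 ≈ 398 on azithromycin. Power is 0.92.

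**Step 3: remove a share *f* of cases.** Excluded women leave numerator and denominator, so the risk in each arm becomes p(1 − f) / [p(1 − f) + (1 − p)]. For rare outcomes the ratio is close to RR × (1 − f_azithromycin) / (1 − f_placebo).

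- 10% of placebo and 20% of azithromycin cases: 0.80 × 0.80 / 0.90 = 0.71.
- 20% and 10%: 0.80 × 0.90 / 0.80 = 0.90.

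The full formula for the maternal outcome gives:

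| Share removed, placebo / azithromycin | Cases removed, placebo / azithromycin | Placebo risk | Azithromycin risk | RR |
|---|---|---|---|---|
| 0% / 0% | 0 / 0 | 3.00% | 2.40% | 0.80 |
| 10% / 10% | 50 / 40 | 2.71% | 2.17% | 0.80 |
| 20% / 20% | 99 / 80 | 2.41% | 1.93% | 0.80 |
| 5% / 10% | 25 / 40 | 2.85% | 2.17% | 0.76 |
| 10% / 20% | 50 / 80 | 2.71% | 1.93% | 0.71 |
| 10% / 5% | 50 / 20 | 2.71% | 2.28% | 0.84 |
| 20% / 10% | 99 / 40 | 2.41% | 2.17% | 0.90 |

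Equal removal of 10% or 20% lowers power from 0.92 to 0.89 or 0.86. With a true RR of 1.00, the pairs 10%/20% and 20%/10% give 0.89 and 1.12.

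**Step 4: can removal be unequal under masking?** Prescribers do not know the arm, but they see the infection. In the US cesarean trial summarized in section 1.6.2 of the protocol, endometritis occurred in 3.8% with azithromycin against 6.1% with placebo, and wound infection in 2.4% against 6.6%. The ratio of endometritis to wound infection was therefore 3.8 / 2.4 ≈ 1.6 with azithromycin and 6.1 / 6.6 ≈ 0.9 with placebo. If the mix of infections differs by arm and drug choice depends on infection type, the share removed can differ by arm with masking intact. This shows a route, not a size.

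**The case against.** The other side has several fair points.

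- **Reach.** Both formal tests use ITT irrespective of protocol deviations. The per-protocol analysis stands beside ITT without imputation and two extreme assumptions about missing outcomes. This stands and sets the limit of the point.
- **Premise.** Nothing says azithromycin is used to treat sepsis at these sites. The protocol sentence on recommended uses goes on to name gonorrhea, chlamydia and *Mycobacterium avium* complex prophylaxis. A reader might infer that the rule certainly deletes outcome cases; the documents show only that it can.
- **Masking.** Clinicians, research staff and women are masked, and equal removal leaves the RR essentially unchanged. A reader might infer that the per-protocol RR is biased; that requires unequal removal, which is possible but not shown.
- **Scope.** The rule names azithromycin, so it should not be read as covering all macrolides. Its reach to infants is unclear because, unlike the ITT, high-risk and as-treated definitions, the per-protocol text does not mention them. Applying a removal share to all neonatal cases would also overstate the effect, since that composite includes intrapartum stillbirth.
- **Purpose.** Excluding placebo women who received the active drug is a legitimate aim. This stands, and it argues against simply deleting the exclusion.
- **Masked review.** It offers a route to settle the matter before unmasking. It is described as dealing with anomalous cases, is not stated to be blind to outcome, and contains no exception for azithromycin given as treatment.

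**Conclusion.** The concern holds as a gap in the definition. As written, the rule can exclude a woman because of the event being counted, and no other section prevents this. The consequence is confined to the per-protocol sensitivity analysis; the ITT tests and the sample size are untouched.

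The size is unknown. If azithromycin is never given for an outcome event, no case is lost this way. If it is given equally often to cases in both arms, incidences and event counts fall while the RR stays at about its true value. If use among cases differs by arm, the RR moves in either direction; 0.71 and 0.90 illustrate a two-fold difference in assumed shares and are not forecasts. These figures also assume that no non-cases are excluded.

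**What to change.** In SAP section 5, or in the planned addendum and before unmasking:

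1. Keep non-study azithromycin as a ground for exclusion only when it was started before any sign or diagnosis of infection.
2. Retain any participant whose primary-outcome event precedes or prompts the drug.
3. State whether the mother's or the infant's azithromycin governs the infant's record. If it is the mother's, a prescription at day 40 could otherwise remove a neonatal outcome already complete at day 28.
4. Report the number of outcome cases excluded from the per-protocol set, by arm and reason.

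**Cost.** Analysts must compare azithromycin start dates with dates of first signs and diagnosis. SAP section 9.2 already derives a sepsis diagnosis date, but it also notes that diagnosis can lag behind occurrence, so the comparison should include first signs. The documents do not state whether start date and indication are recorded for each antibiotic; where they are missing, a default should be fixed under masking. Women given azithromycin for an outcome event stay in the set, which is intended.

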6. SAMPLE SIZE DETERMINATION

6.1 Overall (All-comer) Sample Size for Primary Outcomes

Sample size estimates were generated to evaluate the potential benefits of peripartum prophylactic azithromycin to reduce the risk of adverse maternal and neonatal outcomes in two population cohorts of women in low and low-middle income settings. The first population of interest comprises all women delivering in facilities (overall).

Power calculations for the study in the overall study population were generated for two primary outcome measures, one being the risk of maternal death or sepsis among women in the target population and the other being intrapartum /neonatal death or sepsis in infants delivered by women in the target population. For each of these outcome measures estimates of the required sample size needed to detect a risk reduction of 20%, 25%, and 30% were generated for power of 0.8, 0.85, and 0.9. The risk of sepsis or maternal death was assumed to be 3%. That number is slightly higher than the current risk in the GN population, which is slightly less than 2%. However, we anticipate that with active surveillance rather than passive reporting based on the new WHO

definition of maternal sepsis (designed to catch more cases of sepsis), the risk will be at least 3%. For the neonatal outcome, the underlying risk of the combined outcome of intrapartum stillbirth, neonatal death, or sepsis was assumed to be between approximately 8% and 14%. This estimate was based on recent data from the GN indicating that the risk of intrapartum stillbirth is approximately 1.8% and the risk of neonatal death during the first 28 days after delivery is 2.3%; we assumed that the risk of sepsis not resulting in death is approximately 4% to 10%. The resulting required evaluable sample sizes are shown in Table 1 below.

Table 1. Sample Sizes for the Overall Population, Alpha=0.05

Baseline Risk	Risk Reduction	Evaluable Sample Size per Arm		
		Power=0.80	Power=0.85	Power=0.90
3%	20%	11455	13103	15334
3%	25%	7133	8159	9548
3%	30%	4815	5508	6446
8%	20%	4096	4686	5483
8%	25%	2554	2921	3419
8%	30%	1727	1975	2311
14%	20%	2204	2521	2950
14%	25%	1377	1575	1842
14%	30%	932	1066	1247

The sample sizes shown above assume that the hypothesis test of interest is for the overall population and that the Type 1 error is controlled at the neonatal and maternal hypothesis level via testing each at an alpha = 0.05 level. Interest has been expressed for the overall study for being able to test the neonatal risk separately in south Asia and sub-Saharan Africa. Controlling the Type I error rate at the 0.025 level for each of those two areas within this sub-analysis of neonatal risk will be conducted to avoid multiple comparison concerns. The resulting sample sizes for that comparison are shown in Table 2 below. Note that this sample size would be the size required separately for the African and Asian sites. It is planned that each site will enroll approximately equal number of participants. As such, approximately 37.5% of randomized mothers will be from sub-Saharan Africa and 50% will be from Asia. This planned enrollment distribution is approximately equivalent to the rates of in-facility deliveries observed in the GN registry database. Specifically, approximately a third of the facility deliveries are conducted in sub-Saharan Africa and between 45% and 50% of the facility deliveries are conducted in Asia. These estimates are also consistent with the enrollment rates for the ASPIRIN study that is currently being conducted at these sites. Therefore, to get the total study sample size required, the numbers in the table would need to be multiplied by 3 to achieve reasonable power for the African sites.

Table 2. Sample Sizes Within Region, Alpha=0.025

Baseline risk	Risk Reduction	Evaluable Sample Size per Arm		
		Power=0.80	Power=0.85	Power=0.90
8%	20%	4961	5607	6477
8%	25%	3093	3496	4038
8%	30%	2091	2363	2729

14%	20%	2669	3017	3485
14%	25%	1677	1884	2176
14%	30%	1129	1276	1474

Given the above information, we propose a sample size of 34,000 participants for the overall study. For the primary neonatal outcome of interest of intrapartum/neonatal sepsis or death, assuming that the loss to follow-up will be in the 2% to 3% range (consistent with the current ASPIRIN trial and the Global Network Maternal and Newborn Health registry), this sample size will be sufficient to provide 90% power to detect a 25% reduction in neonatal mortality and sepsis in the sub-Saharan African region and will provide 90% power to detect a 20% reduction in Asia assuming the baseline risk is at least 8%. For the primary maternal outcome of maternal death or sepsis, the sample size will provide 90% power to detect a 20% reduction from 3% in the population aggregated across all study sites.

